4.2 Dose Limiting Toxicity

For the purposes of safety management and defining DLTs, the combination of MGA271 and pembrolizumab, or the combination of MGA271+MGA012 will be treated as one entity. If a DLT is considered related to study drug, no distinction will be made as to which agent is the causative agent and administration of both agents will be stopped. One exception to this rule will be in the circumstance in which a DLT occurs during or immediately following the first pembrolizumab infusion or MGA012 infusion and before the first MGA271 administration. In this case, the toxicity will be attributed to pembrolizumab or MGA012 alone and will not count as a DLT of the combination of study drugs; in this case the patient will be replaced by another patient in the dose cohort.

In general, for patients who experience an AE that may meet the criteria for a DLT, subsequent administration of the study drugs should be held pending management and/or resolution of the event and assessment of attribution to the study drugs. Criteria for subsequent continuation of therapy are outlined below. No dose reductions of either MGA271 or pembrolizumab or MGA012 are allowed during the study.

Dose limiting toxicities will be based on treatment-emergent drug-related AEs (or laboratory abnormalities) occurring during the DLT Evaluation Period (defined as the time following administration of the first dose of pembrolizumab to the day of the third planned administration of pembrolizumab [i.e., Cycle 1/Initial Tumor Assessment Cycle.]) The severity of AEs will be graded according to the National Cancer Institute (NCI) Common Terminology Criteria for Adverse Events (CTCAE) version 4.03.

Dose limiting toxicities are defined separately for hematologic and non-hematologic events as outlined below.

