4.4 Rules for Continuation of Study Therapy

Patients who tolerate treatment with pembrolizumab and MGA271, or who tolerate treatment with MGA271+MGA012, may continue to receive additional treatment with the study drugs as specified in the protocol (see [Section 4.1.1](#)), until any one of the following conditions are met:

- After documentation of a confirmed complete response (cCR), MGA271 and pembrolizumab, or MGA271+MGA012, are continued for one more Tumor Assessment Cycle
- Patient meets criteria for immune-related disease progression (irPD) ([Appendix 6](#))
- Occurrence of drug-related DLT as defined for the DLT Evaluation Period
- The Sponsor, Investigator, or Regulatory Agency terminates the study
- Withdrawal of patient due to an AE or SAE
- Withdrawal of patient consent
- Completion of protocol defined therapy

- Investigator discretion
- Pregnancy
- Death

Note: For individual patients who meet these criteria, but are otherwise considered to be experiencing clinical benefit by the investigator, consideration may be given to extension of therapy on a case-by-case basis in consultation with the Sponsor. If a patient completes 6 cycles of therapy and is experiencing clinical benefit as determined by the investigator, consideration may be given to extension of therapy for an unrestricted number of additional 9-week treatment cycles of MGA271 and pembrolizumab or MGA271+MGA012 on a case-by-case basis in consultation with the Sponsor. Assessments and procedures for Cycles 7 and beyond will be done according to those for Cycle 6 (see [Appendix 1](#)). Such unrestricted treatment may continue until the patient either 1) meets the criteria for permanent discontinuation (see [Section 5.3.1](#)), or 2) a rollover protocol becomes available.

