4.5 Guidelines for Dose Modification

No intra-patient dose escalation will be allowed. No dose reductions will be allowed with exception of 1) reduction of infusion rate during re-challenge for patients experiencing an infusion reaction ([Section 6.5.1](#)) or 2) reduction of dose in patients receiving MGA271 at a dose that is subsequently determined to exceed the MTD ([Section 4.3](#)). For patients who experience DLT that is considered related to either study drug, no further pembrolizumab or MGA271 or MGA012 will be administered.

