4.5.1 Dose Delays

Patients who experience toxicity that is potentially dose-limiting should have study drug held pending assessment, management and resolution of the toxicity. For patients in whom the toxicity is assessed to be unrelated to study drug or for whom the toxicity does not meet the criteria for DLT, therapy may be re-instituted at the same dose and schedule that was administered prior to the event, presuming the toxicity has resolved to \leq Grade 1 in severity. Reinstitution of therapy shall be conducted as follows:

For patients in whom the toxicity is assessed to be related to study drug, dose interruptions of up to 14 days are allowed for drug related toxicity. This may include up to one missed dose of pembrolizumab and up to 2 consecutively missed doses of MGA271. For the MGA271+MGA012 combination, Cohort 4, this would allow for a maximum of one dose each of MGA271 and MGA012. The procedures at the original scheduled missed visit should be performed as soon as possible with treatment reinstated as if no delay had occurred, picking up at the day where the interruption occurred, and patients receive the full complement of pembrolizumab and MGA271 or MGA271+MGA012 or as outlined in The Time and Event Schedule ([Appendix 1](#)). Patients with infusion delays $>$ 14 days due to drug related toxicity will discontinue both study drugs, complete the End of Treatment visit, and then enter the Efficacy Follow-up Period.

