5.3 Withdrawal of Patient from the Trial or Study Drug

5.3.1 Guidelines for Permanent Discontinuation

Patients who meet the following criteria should be permanently withdrawn from study therapy. Patients will continue to be followed as appropriate and consistent with protocol guidelines, but should receive no further study therapy with MGA271 or pembrolizumab or MGA012.

- The patient experiences adverse events that necessitate discontinuation of either study drug.
- The Investigator assesses that the patient's safety is adversely impacted by continuing study therapy.
- Uncontrolled intercurrent illness unrelated to cancer that renders continuing study treatment unsafe or regular study visits impossible.
- The Sponsor, Investigator, or Regulatory Agency terminates the study.
- The patient requests to be discontinued from the study, i.e. withdraws consent.
- Noncompliance with study medication or protocol-required evaluations.
- The patient exhibits progression of disease [according to irRC (i.e., irRECIST)].
- If the patient becomes pregnant during the study, the patient must discontinue study treatment immediately. Reports of pregnancy will be requested until delivery or termination in order to monitor the pregnancy outcome.
- A violation of enrollment criteria or other significant protocol violation is discovered after a patient has been enrolled and treated such that continued treatment would not be in the best interests of the patient.

If the Investigator decides that the patient should be withdrawn from the study or from dosing for any reason other than disease progression, the Sponsor or its designee must be alerted within 24 hours via an Immediately Reportable Event form ([Section 7.9](#)).

Patients who withdraw before Study Day 42 for a reason unrelated to drug toxicity may be considered to have inadequate data to support dose escalation. In this case, replacement patients may be enrolled in the same dose level.

Procedures for handling patients who fail to appear for study visits and criteria regarding when to consider patients lost-to-follow-up will be defined in the Study Procedures Manual.

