- **Grade 3 infusion reaction with MGA271:** If symptoms have resolved to baseline within 12 hours, a re-challenge may be considered at the next scheduled dose, with a 50% reduction of infusion rate. In addition, patients should be pre-medicated for this re-challenge and for any subsequent doses of MGA271 with the following: diphenhydramine hydrochloride 25-50 mg IV, oral acetaminophen 625 mg and hydrocortisone 25-100 mg IV. Patients who have a Grade 3 infusion reaction that does not resolve within 12 hours despite medical management should not receive further MGA271, pembrolizumab, or MGA012 treatment.
- **Grade 3 infusion reaction with pembrolizumab or MGA012:** If the grade 3 infusion reaction occurs with pembrolizumab or with MGA012, both MGA271 and pembrolizumab or MGA271 and MGA012 will be discontinued for that day's dose. If symptoms have resolved to baseline within 12 hours, a pembrolizumab or

MGA012 re-challenge at the next scheduled infusion day may be considered, with a 50% reduction of infusion rate. In addition, patients should be pre-medicated for this re-challenge and for any subsequent doses of pembrolizumab or MGA012 with the following: diphenhydramine hydrochloride 25-50 mg IV, oral acetaminophen 625 mg and hydrocortisone 25-100 mg IV. MGA271 dosing can be resumed with at the next scheduled infusion day if the pembrolizumab or MGA012 grade 3 infusion reaction resolved to grade 1 within 12 hours. Patients who have a Grade 3 infusion reaction that does not resolve within 12 hours despite medical management should not receive further MGA271, pembrolizumab, or MGA012 treatment.

- Patients who experience a second Grade 3 infusion reaction at the time of re-challenge of MGA271 or pembrolizumab or MGA012 (irrespective of duration of first Grade 3 reaction), will permanently discontinue MGA271, and pembrolizumab and MGA012.
- Report as an Immediately Reportable Event (IRE) within 24 hours.
- Report the event as a SAE, if appropriate.

Grade 4

- STOP THE INFUSION AND DISCONNECT THE INFUSION TUBING FROM THE PATIENT.
- TO AVOID EXACERBATION OF INFUSION REACTION OR CRS: DO NOT FLUSH THE TUBING.
- Administer diphenhydramine hydrochloride 50 mg IV, methylprednisolone 2-4 mg/kg IV (or more as considered appropriate), and other medications/treatment as medically indicated (e.g., an IL-6 receptor inhibitor or IL-6 inhibitor, an IL-2 receptor inhibitor, and/or an anti-TNF α antibody).
- Give epinephrine or bronchodilators as indicated.

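### The extension Note in Protocol Section 4.4 exempts no stopping condition, so it conflicts with the firm stops for drug-related DLT and pregnancy and, indirectly, for drug-related delays over 14 days

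*Protocol*

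**What the plan says.** Section 4.4 of the protocol lets patients who tolerate treatment continue until one of ten listed conditions occurs. The list includes drug-related DLT, withdrawal for an AE or SAE, and pregnancy.

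The Note under the list has two parts.

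- **First sentence.** For those "who meet these criteria, but are otherwise considered to be experiencing clinical benefit by the investigator, consideration may be given to extension of therapy", decided case by case after consulting the Sponsor.
- **Second part.** Patients who finish 6 cycles with benefit may be given further 9-week cycles without a set limit. This part has its own limit: "Such unrestricted treatment may continue until the patient either 1) meets the criteria for permanent discontinuation", with a pointer to Section 5.3.1, or until a rollover protocol opens.

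The synopsis repeats the list and both parts of the Note.

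Other sections treat some of the same events as final.

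- **Drug-related DLT.** Section 4.5: "For patients who experience DLT that is considered related to either study drug, no further pembrolizumab or MGA271 or MGA012 will be administered". Section 4.2, and the synopsis in the same words: "no distinction will be made as to which agent is the causative agent and administration of both agents will be stopped".
- **Pregnancy.** Section 5.3.1: "the patient must discontinue study treatment immediately".
- **Delay for drug-related toxicity.** Section 4.5.1: patients with infusion delays of more than 14 "days due to drug related toxicity will discontinue both study drugs, complete the End of Treatment visit" and then enter follow-up.
- **Specific toxicities.** Section 6.5 contains further stops. For example, patients with a second Grade 3 infusion reaction at re-challenge "will permanently discontinue MGA271, and pembrolizumab and MGA012".

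**The concern.** The Note's opening words can only refer to the list directly above them, and nothing is carved out of that list. For a patient with a drug-related DLT or a pregnancy who seems to be benefiting, Section 4.4 invites a discussion about continuing, while Sections 4.5 and 5.3.1 have already closed the question. The protocol states no order of precedence between these sections.

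The stake is patient safety. The Note applies when the Investigator sees benefit, which is when there is most reason to want to continue after a toxicity. Section 4.2 also tells readers handling a possible DLT that continuation criteria come later in the document, and Section 4.4, which carries that title, is where they would look. The synopsis makes this sharper for the other two events: it carries the Note, but neither the 14-day rule of Section 4.5.1 nor the pregnancy instruction of Section 5.3.1.

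**Working it through.** No calculation underlies the conflict itself. The check sets each of the ten conditions in Section 4.4 against any rule for the same event elsewhere in the protocol.

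| Condition in 4.4 | Rule elsewhere | Relation to the Note's first sentence |
|---|---|---|
| Drug-related DLT | 4.2, 4.5 (*will*) | Direct conflict |
| Pregnancy | 5.3.1 (*must*) | Direct conflict |
| Withdrawal for AE or SAE | 4.5.1 for delays over 14 days (*will*); 6.5 toxicity guidelines | Indirect conflict with 4.5.1; softer tension with 6.5 |
| Confirmed irPD | 5.3.1, 7.11.1.1 (*should*) | Intent unclear |
| Consent withdrawn | – | Extension cannot arise |
| Study terminated | – | Extension cannot arise |
| Death | – | Extension cannot arise |
| One cycle after confirmed CR | None found | No firm conflict |
| Protocol therapy completed | Second part of the Note allows more | No firm conflict |
| Investigator discretion | 5.3.1 covers the Investigator's safety judgment (*should*) | No firm conflict |

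Count: 2 direct + 1 indirect + 1 unclear + 3 that cannot arise + 3 without firm conflict = 10.

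Three places could have removed the conflict.

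1. **The pointer to Section 5.3.1.** It is attached to the unrestricted treatment after Cycle 6. It does not reach the first sentence.
2. **The exception in Section 4.2.** "One exception to this rule will be in the circumstance in which a DLT occurs during or immediately following the first pembrolizumab infusion", or the first MGA012 infusion, and before any MGA271. It concerns attribution and replacement of the patient. It has nothing to do with clinical benefit.
3. **The opening of Section 4.4.** It restricts the section to patients who tolerate treatment. But DLT, AE or SAE withdrawal and pregnancy are in the section's own list, so they stay within the Note's reach.

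**Patients still exposed.** Section 2.3.1.1.2 reports that the pembrolizumab cohorts are closed and their patients have completed combination treatment, which leaves mainly Cohort 4. Section 4.1.2 caps that cohort at 15 dose-evaluable patients if 15 mg/kg is tolerated. Suppose instead that 15 and 10 mg/kg both exceed the MTD within the 9-patient limit of the 3+3+3 rule, and 3 mg/kg is then expanded to 15. The ceiling is then 9 + 9 + 15 = 33, before replacements.

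**The case against.** The best defence is that the Note only permits consideration. An extension can be requested, considered and refused because Section 4.5 or 5.3.1 forbids it, so every sentence can be obeyed. Section 4.4 also refers back to Section 4.1.1, which allows further cycles only when there has been no toxicity severe enough to force a permanent stop. Section 7.8.2.6 requires pregnancies and AEs leading to permanent discontinuation to reach the Sponsor within 24 hours, so the Sponsor would know of the event when consulted. Finally, a fully literal reading would cover death and withdrawn consent, which suggests that the authors had irPD, complete response or completed therapy in mind.

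Much of this stands. A reader might infer that the Note authorises dosing after a DLT or in pregnancy. The documents do not support that: the stops keep their force and Section 4.1.1 still applies. What does not stand is that the text is therefore consistent. Section 4.1.1 does not amend the Note, and offering case-by-case consideration of something another section rules out is still a contradiction. The likely intent is plausible but is not written down.

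A reader might also infer that the Note contradicts every toxicity stop in Section 6.5 equally. That goes too far. Those stops enter only through the AE or SAE bullet. Section 6.5.2 calls its rules general guidelines, and Section 6.5.1.3 lets the Investigator modify its own. Case-by-case judgment sits uneasily with them but does not contradict them outright. The 14-day rule in Section 4.5.1 also enters through that bullet, but its wording is mandatory.

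**Conclusion.** The point holds in limited form. The first sentence of the Note conflicts directly with the stops for two events (drug-related DLT and pregnancy) and indirectly with a third (drug-related delay over 14 days). The indirect limb assumes that a patient stopped under Section 4.5.1 counts as withdrawn for an AE or SAE. Section 6.5 is a softer tension only. For confirmed irPD, the protocol leaves open whether extension is meant.

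This is an internal contradiction on a safety rule that should be fixed. A reader might go on to infer distorted DLT counts or MTD decisions, or biased efficacy results. Nothing in the documents shows such an effect, and none is claimed.

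The figure of 15, or 33 under the de-escalation assumption, is a ceiling on the patients still exposed and does not estimate the number affected. An affected patient would need both one of these stops and Investigator-judged benefit. How often that would happen cannot be derived from the documents.

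**What to change.** Directly after the first sentence of the Note, in Section 4.4 and in the synopsis, add:

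*This does not apply to patients with a drug-related DLT (Sections 4.2, 4.5), pregnancy (Section 5.3.1), or a drug-related dosing delay of more than 14 days (Section 4.5.1); for these patients study treatment is permanently discontinued.*

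Do not cite Section 5.3.1 or Section 6.5 as a whole. Section 5.3.1 includes progression by irRC, so a blanket reference would bar extension after irPD without anyone having decided that. A blanket reference to Section 6.5 would turn guidance that is partly modifiable into an absolute rule.

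Decide separately whether extension after confirmed irPD is intended. If it is, add *except as allowed in Section 4.4* to the irRC-progression bullet in Section 5.3.1 and to the irPD stop in Section 7.11.1.1.

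The cost is one sentence in two places, plus two short insertions if irPD extension is wanted. It needs Sponsor approval and, where required, prior written IRB/IEC approval under Section 11.1. It adds no visits, patients or analyses.

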4.5 Guidelines for Dose Modification

No intra-patient dose escalation will be allowed. No dose reductions will be allowed with exception of 1) reduction of infusion rate during re-challenge for patients experiencing an infusion reaction ([Section 6.5.1](#)) or 2) reduction of dose in patients receiving MGA271 at a dose that is subsequently determined to exceed the MTD ([Section 4.3](#)). For patients who experience DLT that is considered related to either study drug, no further pembrolizumab or MGA271 or MGA012 will be administered.

4.5.1 Dose Delays

Patients who experience toxicity that is potentially dose-limiting should have study drug held pending assessment, management and resolution of the toxicity. For patients in whom the toxicity is assessed to be unrelated to study drug or for whom the toxicity does not meet the criteria for DLT, therapy may be re-instituted at the same dose and schedule that was administered prior to the event, presuming the toxicity has resolved to \leq Grade 1 in severity. Reinstitution of therapy shall be conducted as follows:

For patients in whom the toxicity is assessed to be related to study drug, dose interruptions of up to 14 days are allowed for drug related toxicity. This may include up to one missed dose of pembrolizumab and up to 2 consecutively missed doses of MGA271. For the MGA271+MGA012 combination, Cohort 4, this would allow for a maximum of one dose each of MGA271 and MGA012. The procedures at the original scheduled missed visit should be performed as soon as possible with treatment reinstated as if no delay had occurred, picking up at the day where the interruption occurred, and patients receive the full complement of pembrolizumab and MGA271 or MGA271+MGA012 or as outlined in The Time and Event Schedule ([Appendix 1](#)). Patients with infusion delays $>$ 14 days due to drug related toxicity will discontinue both study drugs, complete the End of Treatment visit, and then enter the Efficacy Follow-up Period.

4.6 Rationale for Study Design

As described in **Sections 2.4 and 2.5**, there is a strong rationale to evaluate the antitumor activity of the MGA271 and pembrolizumab/MGA012 combination in advanced melanoma, NSCLC, SCCHN, and urothelial cancer. The study is designed to determine the MTD or MAD of the combination in the Dose Escalation Phase of the study in multiple tumor types. In Cohort 4, the combination of MGA271+MGA012 will be explored in patients with the same tumor types explored in the MGA271+pembrolizumab dose escalation cohorts, i.e., mesothelioma, urothelial cancer, NSCLC, SCCHN, ccRCC, ovarian cancer, melanoma, thyroid cancer, TNBC, pancreatic cancer, colon cancer, soft tissue sarcoma, or prostate cancer; justification provided in **Section 2.5**. The DLT Evaluation period occurs within the first Tumor Assessment Cycle; patients who do not experience a DLT or other unacceptable toxicity will then be allowed to continue receiving MGA271 and pembrolizumab or MGA271+MGA012 for up to 5 additional 9-week Tumor Assessment Cycles. Once an MAD or MTD is defined, patients will be enrolled into an Expansion Phase.

4.7 Study Duration

MGA271 will be administered on a once weekly schedule for up to 51 doses and pembrolizumab administered once every 3 weeks for a total of up to 17 doses (i.e., up to 6 cycles). Beginning with Amendment 5, MGA271 will be administered on a Q3W schedule for up to 17 doses of MGA271 and MGA012 administered once every 3 weeks for a total of up to 17 doses (i.e., up to 6 cycles). As per Rules for Continuation of Study Therapy (**Section 4.4**), an unrestricted number of additional cycles may be permitted on a case-by-case basis in consultation with the Sponsor.

It is expected that enrollment of the dose escalation portion of the study will occur over approximately 12 months, and that enrollment of the cohort expansion portion of the study will take approximately 9 - 12 months.

The total time for conduct of the trial is expected to be approximately 72 months (which includes 24 weeks of efficacy follow-up). These estimates of the timing for study conduct may vary from that observed in the actual conduct of the trial.

4.7.1 Patient Accrual

The number of patients enrolled in the Dose Escalation Phase cannot be precisely determined in advance, and could range from 9 to 45 or more patients depending on results in the course of the trial and the number of MG271 doses explored. This patient number does not take into account patient replacement for non-evaluable patients or the possibility of expanding an individual escalation cohort to 15 patients to allow for further evaluation of safety, PK and antitumor activity of the combination of MGA271 and pembrolizumab at the dose level in that cohort.

The Cohort Expansion Phase of the trial will enroll 112 patients, with a target of 16 to 20 patients into each of 6 cohorts: two cohorts of patients with NSCLC (up to 20 patients in each cohort), two cohorts of patients with SCCHN (up to 20 patients in each cohort), one

cohort of patients with melanoma (up to 16 patients), and one cohort of patients with urothelial cancer (up to 16 patients). This number of patients does not take into account patients who may be replaced. During the Expansion Portion of the study, patients who withdraw before completing the first tumor assessment for a reason other than progression of disease may be considered unevaluable for response. In these cases, replacement patients may be enrolled in the same dose level as required to complete the cohort.

For planning, the maximum number of patients to be enrolled on this trial is anticipated to be approximately 157 patients.

